6.13.2.4. Thyroid Malignancies and C-Cell Hyperplasia

Treatment-emergent thyroid disease, C-cell hyperplasia, and neoplasms will be identified using pre-defined MedDRA high level terms (HTLs) of thyroid neoplasms, and PT of C-cell hyperplasia. Detailed searching criteria can be found in [Appendix 1](#). A summary by treatment and PT/PT within HLT and a listing will be provided. Thyroid malignancies and C-cell hyperplasia will be considered as AESIs.

6.13.2.4.1. Calcitonin

Observed calcitonin data will be summarized by treatment and nominal visit. The number and proportion of patients with a maximum postbaseline calcitonin value exceeding the following thresholds will be provided by treatment and baseline calcitonin value (≤ 20 , >20 to ≤ 35 ng/L, >35 ng/L): ≤ 20 ng/L, >20 to ≤ 35 ng/L, >35 to ≤ 50 ng/L, >50 to ≤ 100 ng/L, >100 ng/L.

6.13.2.5. Malignancies

The AE database will be searched using pre-defined SMQs to identify events consistent with malignancy. Detailed searching criteria can be found in [Appendix 1](#). A summary by treatment and PT within SMQ and a listing of TEAEs will be provided. Malignancy will be considered as an AESI.

6.13.2.6. Major Adverse Cardiovascular Events

Major adverse cardiovascular events (MACE) reported by investigators are adjudicated by an independent CEC in a blinded fashion. The MACE of special interest are: deaths due to cardiovascular cause, myocardial infarction, hospitalization for unstable angina, hospitalization for heart failure, coronary interventions (such as coronary artery bypass graft [CABG] or percutaneous coronary intervention [PCI]); and cerebrovascular events, including cerebrovascular accident (stroke) and transient ischemic attack (TIA).

A listing of patients reporting MACE, either reported by investigator or identified by the CEC, will be provided. The listing will include treatment, patient identification including the site number, date of event, type of event as reported by the investigator, type of event as adjudicated by the CEC, time from first dose of study drug to the event, and time from the last dose to the event (if patient has discontinued study drug prior to the event). Only adjudication-confirmed MACE will be considered as AESIs.

6.13.2.7. Supraventricular Arrhythmias and Cardiac Conduction Disorders

The AE database will be searched using pre-defined SMQ or MedDRA HLT to identify events consistent with supraventricular arrhythmias and cardiac conduction disorders. Detailed searching criteria can be found in [Appendix 1](#). Incidence of the resulting TEAEs will be summarized by treatment and PT. Treatment-emergent severe/serious supraventricular arrhythmias and cardiac conduction disorders will be considered as AESIs.

6.13.2.8. Hypersensitivity Events

Hypersensitivity reactions and related information reported via the “Hypersensitivity and Anaphylactic Reactions” eCRF will be summarized by treatment. Two main analyses are performed:

- **Potential Immediate Hypersensitivity:** Analysis of TEAEs occurring from the start of study drug administration up to 24 hours after the end of study drug administration.
- **Potential Non-Immediate Hypersensitivity:** Analysis of TEAEs occurring more than 24 hours after the end of study drug administration, but prior to subsequent study drug administration.

All potential hypersensitivity reactions will be reported by PT within SMQ. Preferred Term will be used for the summary within each category in decreasing order of incidence. Detailed searching criteria for hypersensitivity events can be found in [Appendix 1](#). The serious/severe cases of hypersensitivity will be considered as AESIs.

6.13.2.9. Injection Site Reactions

Injection site reactions, incidence and rates, and related information reported via the “Injection Site Reactions” eCRF will be summarized by treatment. Information to be summarized includes the timing of the reaction relative to study drug administration, and characteristics of the injection site reaction: erythema, induration, pain, pruritus, and edema.

Additionally, potential injection site reactions will be reported by PT within MedDRA HLTs of injection site reactions and administration site reactions. The PT will be used for the summary within each category in decreasing order of incidence. Only the severe/serious injection site reactions will be considered as AESIs.

6.13.2.10. Anti-Drug Antibodies

6.13.2.11. Diabetic Retinopathy Complications

Results of the baseline dilated fundoscopic exam will be summarized by treatment. Any TEAE suspected of worsening retinopathy triggers a follow-up dilated fundoscopic exam. A summary of TEAEs suspected of worsening retinopathy and a summary of change from baseline in dilated fundoscopic exam will be summarized by treatment and PT.

The cases with repeat fundoscopy during the course of the trial, based on clinical suspicion of worsening retinopathy that have either findings of de novo retinopathy or progression of retinopathy, and severe/serious adverse events from the PTs defined in searching criteria in [Appendix 1](#) will be considered as AESI and summarized.

6.13.2.12. Hepatic Safety

6.13.2.12.1. Hepatobiliary Disorders

The AE database will be searched using SMQs to identify events consistent with hepatobiliary disorders. Detailed searching criteria can be found in [Appendix 1](#). A summary by treatment and PT within SMQ will be provided. Severe/serious hepatobiliary disorders will be considered as AESI.

6.13.2.12.2. Acute Gallbladder Disease

The AE database will be searched using pre-defined SMQs to identify events consistent with acute gallbladder diseases. Severe/serious acute gallbladder disease will be considered as AESIs. Detailed searching criteria for these AEs can be found in [Appendix 1](#).

6.13.2.12.3. Liver Enzymes

Analyses for laboratory analyte measurements are described in Section [6.13.5](#). This section describes additional analyses of liver enzymes. The following will be provided by treatment group:

- A shift table of maximum to maximum alanine aminotransferase (ALT) measurement from baseline to postbaseline. Baseline categories include \leq ULN, $>1 \times$ ULN and missing.

Postbaseline categories include \leq ULN, >1 to $<3 \times$ ULN, ≥ 3 to $<5 \times$ ULN, ≥ 5 to $<10 \times$ ULN, $\geq 10 \times$ ULN.

- A shift table of maximum to maximum aspartate transaminase (AST) measurement from baseline to postbaseline. Baseline categories include \leq ULN, $>1 \times$ ULN and missing. Postbaseline categories include \leq ULN, >1 to $<3 \times$ ULN, ≥ 3 to $<5 \times$ ULN, ≥ 5 to $<10 \times$ ULN, $\geq 10 \times$ ULN.
- Shift tables of maximum to maximum total bilirubin and direct bilirubin from baseline to postbaseline with the following categories: \leq ULN, >1 to $<2 \times$ ULN, $\geq 2 \times$ ULN.
- Shift tables of serum alkaline phosphatase (ALP) from baseline to postbaseline with the following categories: \leq ULN, >1 to $<2 \times$ ULN, $\geq 2 \times$ ULN.

Maximum baseline will be the maximum non-missing observation in the baseline period. The maximum value will be the maximum non-missing value from the postbaseline period. Planned and unplanned measurements will be included.

6.13.2.13. Severe Gastrointestinal Adverse Events

Summaries of all events of treatment-emergent gastrointestinal (GI) AEs, including nausea, vomiting, and diarrhea will be provided by treatment and PT with decreasing frequency.

The time courses of prevalence and incidence (newly-occurring episodes) of GI AEs (nausea and/or vomiting and/or diarrhea) will be plotted by treatment and maximum severity.

The maximum severity and duration of treatment-emergent nausea and/or vomiting and/or diarrhea through the end of the study will be summarized by treatment.

Preferred Terms with serious/severe cases in the gastrointestinal SOC will be considered as AESIs.

6.13.2.14. Acute Renal Events

Laboratory measures related to renal safety will be analyzed as specified for laboratory measurements in Section [6.13.5](#).

Two shift tables examining renal function will be created. A min-to-min shift table of eGFR estimated by the Chronic Kidney Disease Epidemiology Collaboration (CKD-EPI) equation with units mL/min/1.73 m², using categories (<30 , ≥ 30 to <45 , ≥ 45 to <60 , ≥ 60 to <90 , and ≥ 90 mL/min/1.73 m²). A max-to-max shift table of urine albumin-to-creatinine ratio (UACR), using the categories UACR <30 mg/g, 30 mg/g \leq UACR ≤ 300 mg/g, UACR >300 mg/g (respectively, these represent normal, microalbuminuria, and macroalbuminuria).

To examine AEs for any suggestion of decrease in renal function, summary of acute renal failure searched by MedDRA SMQ will be presented. Detailed searching criteria can be found in [Appendix 1](#). Severe/serious acute renal events will be considered as AESIs.

6.13.2.15. Dehydration

The AE database will be searched using SMQ of dehydration to identify events consistent with dehydration. Detailed searching criteria can be found in [Appendix 1](#). Severe/serious dehydration events will be considered as AESIs.

6.13.2.16. Metabolic Acidosis, Including Diabetic Ketoacidosis

The AE database will be searched using MedDRA PT to identify events consistent with metabolic acidosis. Detailed searching criteria can be found in [Appendix 1](#). The incidence of the resulting TEAEs will be summarized by treatment and PT. Severe/serious metabolic acidosis, including diabetic ketoacidosis will be captured as AESIs.

6.13.2.17. Amputation/Peripheral Revascularization

The AE database will be searched using MedDRA PT to identify events consistent with amputation or peripheral revascularization. The incidence of the resulting TEAEs will be summarized by treatment and PT. Amputation/peripheral revascularization will be considered as AESIs.

6.13.2.18. Major Depressive Disorder/ Suicidal Ideation

The AE database will be searched using SMQs to identify events consistent with major depressive disorder or suicidal ideation. Detailed searching criteria can be found in [Appendix 1](#). The incidence of the resulting TEAEs will be summarized by treatment and PT. Severe/serious major depressive disorder/suicidal ideation or behavior will be considered as AESIs.

6.13.3. Vital Signs

Descriptive summaries at the screening visit will be summarized for the enrolled population. Descriptive summaries by treatment and by nominal visit will be provided for baseline (with respect to the treatment period) and postbaseline values as well as change from baseline values. If 2 records are taken at the same visit, they will be averaged prior to being used for data summaries and analyses.

An MMRM using REML will be used to fit the changes from baseline in vital signs at all scheduled postbaseline visits. The model will include treatment, visit, treatment-by-visit interaction, country/pooled country, baseline HbA1c ($\leq 8.5\%$, $>8.5\%$ [≤ 69 , >69 mmol/mol]), and baseline metformin use (Yes/No) as fixed effects, and baseline value of the dependent variable as a covariate.

Counts and percentages of patients with treatment-emergent abnormal sitting systolic blood pressure (BP), sitting diastolic BP, and pulse will be presented by treatment. The criteria for identifying patients with treatment-emergent vital sign abnormalities are stated in [Table GPHD.6.4](#).

Table GPHD.6.4. Categorical Criteria for Abnormal Treatment Emergent Blood Pressure and Pulse Measurements

| Parameter | Low | High |
|--|--|---|
| Systolic BP (mm Hg) (Supine or sitting – forearm at heart level) | ≤ 90 and decrease from baseline ≥ 20 | ≥ 140 and increase from baseline ≥ 20 |
| Diastolic BP (mm Hg) (Supine or sitting – forearm at heart level) | ≤ 50 and decrease from baseline ≥ 10 | ≥ 90 and increase from baseline ≥ 10 |
| Pulse (bpm) (Supine or sitting) | <50 and decrease from baseline ≥ 15 | >100 and increase from baseline ≥ 15 |

Abbreviation: BP = blood pressure.

6.13.4. *Electrocardiograms*

No statistical analysis will be conducted for ECG parameters in this study.

6.13.5. *Clinical Laboratory Evaluation*

All laboratory data will be reported in the International System of Units. Selected laboratory measures will also be reported using conventional units. Values that are outside of reference ranges will be flagged as high (H) or low (L) in the listings. Descriptive summaries by treatment and by nominal visit will be provided for the baseline (with respect to the treatment period) and postbaseline values as well as the change from baseline values. If applicable, descriptive summaries for the screening visit will be provided for the enrolled population.

Observed and change from baseline values for selected measurements for each visit will be displayed graphically for patients who have both a baseline and a postbaseline planned measurement. Unplanned measurements will be excluded from graphs.

Shift tables will be produced for selected measurements. A shift table will include unplanned measurements. The shift table will include the number and percentage of patients within each baseline category (low, normal, high, or missing) versus each postbaseline category (low, normal, high, or missing) by treatment. The proportion of patients shifted will be compared between treatments.

For qualitative laboratory analytes, the number and percentage of patients with normal and abnormal values will be summarized by treatment.

A listing of abnormal findings will be created for laboratory analyte measurements, including qualitative measures. The listing will include patient ID, treatment group, laboratory collection date, study day, analyte name, and analyte finding.

6.14. *Health Outcomes*

The patient-reported outcome questionnaires will be completed by the patients at baseline and at 52 weeks (or early termination visit prior to 52 weeks). These include use of the mITT

population on the FAS, and use of a 2-sided alpha level of 0.05 and a 2-sided 95% CI for pairwise comparisons.

No multiplicity adjustment will be made in the evaluation of health outcome measures. Item-level missingness is dealt with as per the instrument developer's instruction.

6.14.1. Short-Form-36 Health Survey Version 2, Acute Form

The SF-36v2 acute, 1-week recall version is a 36-item, generic, patient-completed measure designed to assess the following 8 domains:

- Physical Functioning
- Role-Physical
- Bodily Pain
- General Health
- Vitality
- Social Functioning
- Role-Emotional
- Mental Health

The Physical Functioning domain assesses limitations due to health "now" while the remaining domains assess functioning "in the past week." Each domain is scored individually and information from these 8 domains are further aggregated into 2 health-component summary scores: Physical Component Summary and Mental Component Summary. Items are answered on Likert scales of varying lengths (3-, 5-, or 6- point scales). Scoring of each domain and both summary scores are norm-based and presented in the form of T-scores, with a mean of 50 and SD of 10; higher scores indicate better levels of function and/or better health (Maruish 2011).

Per copyright owner, the QualityMetric Health Outcomes™ Scoring Software 4.5 will be used to derive the domains and component summary scores from the raw scores. Each domain and component summary scores will be summarized descriptively by treatment at each scheduled visit at which the SF-36v2 is administered. The changes from baseline to week 52 (last observation after baseline carried forward [LOCF]) in each domain and component summary scores will be analyzed using ANCOVA models with model terms of treatment, country/pooled country, baseline HbA1c ($\leq 8.5\%$, $> 8.5\%$ [≤ 69 , > 69 mmol/mol]) and baseline metformin use (Yes/No) as fixed effects, and the corresponding baseline score as a covariate.

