9.4.3.3. Tertiary/Exploratory Analyses

All exploratory efficacy analyses will be guided by the “efficacy” estimand without imputation of missing data and will be conducted using the EAS. Details will be provided in the SAP.

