6.4. Handling of Dropouts or Missing Data

For the primary and secondary efficacy endpoint analyses relative to treatment-regimen estimand and subject to type 1 error rate control, data for participants with missing values at the 52-week visit will be imputed based on the method described in Section 6.12.1.3. For analysis relative to efficacy estimand, missing values will be considered missing at random. Unless specified otherwise, imputation of missing data will be limited to primary and key secondary efficacy endpoint analyses. Any other secondary or exploratory efficacy parameter values or safety laboratory values that are missing will not be explicitly imputed.

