6.12.4. Other Secondary and Exploratory Efficacy Analyses

Other secondary and exploratory efficacy measures will use the efficacy estimand and will be summarized by treatment and nominal visit. Missing data will not be explicitly imputed and assessments are not subject to type 1 error rate control. Some parameters may be log transformed, if necessary.

Table GPHD.6.2. Secondary and Exploratory Efficacy Analyses not Controlled for Type I Error

| Objective | Relative to the efficacy measure: | Analysis Conducted in a manner similar to section: | Additional Information |
|--|--|--|--|
| Secondary Analyses | | | |
| To evaluate superiority of tirzepatide (5 mg, 10 mg, and/or 15 mg) QW to insulin lispro (U100) at 52 weeks in: | Proportion of participants achieving an HbA1c target value of <7% (53 mmol/mol) | 6.12.2.3 | None |
| To evaluate superiority of tirzepatide (pooled cohort of 5 mg, 10 mg, and 15 mg) QW to insulin lispro (U100), And to evaluate superiority of tirzepatide 5 mg, 10 mg, and/or 15 mg QW to insulin lispro (U100) at 52 weeks in: | Proportion of participants achieving an HbA1c target value of $\leq 6.5\%$ (48 mmol/mol) | 6.12.2.3 | None |
| | Mean change in fasting serum glucose (central laboratory) from baseline | 6.12.1.1 | Use baseline HbA1c category ($\leq 8.5\%$, $>8.5\% [\leq 69, >69 \text{ mmol/mol}]$) in place of baseline HbA1c. Use baseline FSG as a covariate. |
| | Change from baseline in 7-point self-monitored blood glucose (SMBG) profiles | 6.12.1.1 | Use baseline SMBG as a covariate. LSM estimates at 52-weeks will be summarized by treatment and 7-points. |

| Objective | Relative to the efficacy measure: | Analysis Conducted in a manner similar to section: | Additional Information |
|-----------|---|---|--|
| | | | In addition to the analyses on each of the 7-points, similar analyses will be done for the 2-hour morning, midday, and evening meal excursions, the mean of all meals 2-hour excursion, the mean of all 7-point measurements, the mean of all pre-meal measurements, and the mean of all 2-hour postprandial measurements. |
| | Proportion of participants who achieved HbA1c target value of <7.0% (53 mmol/mol) without hypoglycemia (confirmed glucose <54 mg/dL [3.0 mmol/L] or report of severe hypoglycemia) | 6.12.2.3 | Severe hypoglycemia follows ADA level 3 definition. |

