| | Proportion of patients who achieved weight loss of $\geq 5\%$, from baseline | 6.12.2.3 | Use baseline HbA1c category ($\leq 8.5\%$, $>8.5\% [\leq 69, >69 \text{ mmol/mol}]$) as in place of baseline HbA1c. Use baseline weight as a covariate. |
| | Mean change from randomization in SF-36v2 acute form Physical Component summary score Mental Component summary score Physical Functioning domain score General Health domain score Vitality domain score Role-Physical domain score Bodily Pain domain score | 6.12.1.2 | Use ANCOVA. Use baseline HbA1c category ($\leq 8.5\%$, $>8.5\% [\leq 69, >69 \text{ mmol/mol}]$) as in place of baseline HbA1c. Use corresponding baseline score as a covariate. |

| Objective | Relative to the efficacy measure: | Analysis Conducted in a manner similar to section: | Additional Information |
|--|---|---|---|
| | Social Functioning domain score Role-Emotional domain score Mental Health domain score | | |
| Exploratory Objectives | | | |
| To evaluate superiority of tirzepatide (pooled cohort of 5 mg, 10 mg, and 15 mg) QW to insulin lispro (U100) at 52 weeks in: | Change from baseline in lipid parameters (Total-Cholesterol, HDL-C, LDL-C, VLDL-C, TG) | 6.12.1.1 | Use baseline HbA1c category ($\leq 8.5\%$, $>8.5\% [\leq 69, >69 \text{ mmol/mol}]$) in place of baseline HbA1c. Use corresponding baseline lipid parameter as a covariate |
| | Change from baseline in waist circumference | 6.12.1.1 | Use baseline HbA1c category ($\leq 8.5\%$, $>8.5\% [\leq 69, >69 \text{ mmol/mol}]$) in place of baseline HbA1c. Use baseline waist circumference as a covariate |
| | Change from baseline in BMI | 6.12.1.1 | Use baseline HbA1c category ($\leq 8.5\%$, $>8.5\% [\leq 69, >69 \text{ mmol/mol}]$) in place of baseline HbA1c. Use baseline BMI as a covariate. |

| Objective | Relative to the efficacy measure: | Analysis Conducted in a manner similar to section: | Additional Information |
|-----------|--|--|---|
| | Change from baseline in patient reported outcomes: APPADL, IW-SP, EQ-5D-5L | 6.12.1.2 | Use ANCOVA. Use baseline HbA1c category ($\leq 8.5\%$, $>8.5\% [\leq 69, >69 \text{ mmol/mol}]$) as a fixed effect. Use corresponding baseline patient outcome score as a covariate. |

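### The SAP gives the patient-reported outcomes two conflicting rules: efficacy estimand without imputation in 6.12.4, but full analysis set with LOCF in 6.14 to 6.14.4

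*SAP*

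**What the plan says.** **One rule.** SAP 6.12.4 states: "Other secondary and exploratory efficacy measures will use the efficacy estimand and will be summarized by treatment and nominal visit". It continues: "Missing data will not be explicitly imputed and assessments are not subject to type 1 error rate control". Table GPHD.6.2, in the same section, lists the ten SF-36v2 scores as secondary measures and APPADL, IW-SP and EQ-5D-5L as exploratory. SAP 6.2 ties the efficacy estimand to the EAS. SAP 6.4 says that, unless specified otherwise, "imputation of missing data will be limited to primary and key secondary efficacy endpoint analyses"; none of these instruments is primary or key secondary. For the exploratory instruments, Protocol 9.4.3.3 agrees: analyses follow the efficacy "estimand without imputation of missing data and will be conducted using the EAS".

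**The other rule.** SAP 6.14 calls for the mITT "population on the FAS, and use of a 2-sided alpha level of 0.05". SAP 6.14.1 then defines the SF-36v2 analysis: "The changes from baseline to week 52 (last observation after baseline carried forward [LOCF". Sections 6.14.2 to 6.14.4 apply LOCF to EQ-5D-5L, IW-SP and APPADL.

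**A pointer between them.** Table GPHD.6.2 sends these rows to 6.12.1.2 with the instruction "Use ANCOVA. Use baseline HbA1c category". Section 6.12.1.2 is the treatment-regimen analysis of HbA1c, run on the FAS with multiple imputation.

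Protocol 9.4.3.2 promises linear models for patient-reported outcomes and leaves further model terms to the SAP. It sets no data set and no missing-data rule.

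**The concern.** Two programmers could follow the SAP faithfully and report different SF-36v2 results from different sets of scores. The SF-36v2 objective covers ten scores, each compared for the pooled cohort and for three doses: 10 × (1 + 3) = 40 named secondary comparisons. The scores are self-reported in an open-label trial, so the choice of analysis should be settled in the plan before the data are seen.

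LOCF adds a problem of its own. Seven SF-36v2 domains ask about the past week and the eighth asks about now. A score taken at withdrawal describes the days around withdrawal. Reporting it as Week 52 misstates what was measured.

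**Working it through.** **1. The plan's own figure.** There is none for any patient-reported outcome. The only sizing figures are for HbA1c noninferiority (SD 1.3%, margin 0.3%, one-sided 0.025). They reproduce by noncentral t as 80.0% per dose (197 v 591; stated 80%) and 97.7% pooled (591 v 591; stated 97%). They do not bear on this point.

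**2. The two rules side by side.**

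| | SAP 6.12.4 (with 6.1, 6.2, 6.4) | SAP 6.14 to 6.14.4 |
|---|---|---|
| Estimand | Efficacy | Not named; 6.2 pairs the FAS with treatment-regimen |
| Data set | EAS | FAS |
| Week 52 score after stopping drug or after rescue | Excluded | Included |
| Missing Week 52 score | Left missing | Replaced by the early-termination score, if there is one |
| Model | ANCOVA, through Table GPHD.6.2 | ANCOVA |

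The model agrees. Estimand, data set and missing-data handling do not.

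**3. What LOCF can carry.** The protocol's Schedule of Activities marks the four questionnaires at Visit 6, Visit 23 and early termination, and SAP 6.14 says the same. There is no intermediate visit, and the follow-up table lists no questionnaire. The only post-baseline score available before Week 52 is the early-termination score. Where none was taken, LOCF fills nothing.

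**4. Whom it touches.** Under Protocol 7.1, a participant who stops study drug stays in the study and completes all visits, so a real Week 52 score is due. Under Protocol 7.2, the early-termination visit takes place on leaving the study, where possible. LOCF therefore acts only on people who leave. Those who stop drug and stay are affected by the choice between EAS and FAS instead.

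**5. How many scores (assumed shares).** The documents give no withdrawal rate. If 5%, 10% or 15% of 1182 leave with a completed questionnaire, then 0.05 × 1182 = 59, 0.10 × 1182 = 118 or 0.15 × 1182 = 177 scores are relabelled.

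**6. Do the rules give different answers? (every input assumed)** For one arm, let m be the mean Week 52 change on drug, d the share leaving with an early-termination score, s the share off drug but followed, g the fraction of m kept off drug, and f the change at early termination as a fraction of m.

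- EAS, observed: m
- FAS, observed: [(1 − d − s)m + s·g·m] / (1 − d)
- FAS with LOCF: (1 − d − s)m + s·g·m + d·f·m

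Take m = 3 T-score points for tirzepatide and 0 for lispro, so that all lispro terms vanish. With d = 0.10, s = 0.05, g = 0.3 and f = 0.5:

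- EAS: 3.00
- FAS, observed: (2.55 + 0.045) / 0.90 = 2.88
- FAS with LOCF: 2.55 + 0.045 + 0.15 = 2.745

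Letting d run from 5% to 15%, s from 5% to 10% and f from −0.5 to 0.5, the estimated difference is 3.00 on the EAS, 2.75 to 2.89 on the FAS as observed, and 2.11 to 2.82 on the FAS with LOCF. The downward direction under LOCF is built in by taking f no higher than 0.5; a larger early-termination change could reverse it. The illustration shows only that the rules need not agree.

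**The case against.** **The specific section governs the general one.** Section 6.14 is written for these instruments, and 6.4 allows exceptions. This is the best defence, and a reader could adopt it. However, the no-imputation sentence in 6.12.4 carries no exception, its own table names these instruments, and 6.14 never says which estimand it serves. The conflict is not resolved on the page.

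**The table pointer is only about the model.** This stands. A reader might infer three incompatible rules by treating the pointer to 6.12.1.2 as importing the treatment-regimen estimand and multiple imputation. The column describes analyses done in a similar manner, the row names no data set or missing-data method, and 6.4 keeps imputation away from these measures by default. Model form is the natural reading. The pointer adds ambiguity, not a third rule.

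**LOCF is an estimator, not an estimand.** This also stands. Using the FAS regardless of adherence fits the treatment-regimen estimand, and LOCF is a weak way of filling gaps within it. SAP 6.14 also discloses that the second questionnaire may come from early termination. The label Week 52 is still wrong for such a score.

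**Few people are affected.** Protocol 7.2 expects discontinuation to be uncommon, and these outcomes carry no multiplicity-controlled claim. Both limit the consequence.

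**Conclusion.** The point holds as a conflict between two rules for the same scores: EAS with no explicit imputation in 6.12.4, and FAS with LOCF in 6.14 to 6.14.4. As written, the plan does not determine who is analysed or what happens to a missing score. Separately, LOCF labels early-termination scores as Week 52 scores for participants who leave the study.

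No reliable size can be given. The ranges in the working rest entirely on assumed effects and withdrawal shares. The primary and key secondary results are untouched.

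A reader might go further and infer that LOCF biases the comparison because gastrointestinal intolerance drives dropout on tirzepatide. The documents do not support that. Protocol 6.6.3 and 7.1 keep people who stop tirzepatide for such symptoms in the study, with all planned measurements, and nothing in the documents shows that study withdrawal will differ between arms.

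**What to change.** Name one estimand and one data set for the patient-reported outcomes, in the same words in SAP 6.12.4, Table GPHD.6.2 and 6.14. Say that the table's pointer to 6.12.1.2 concerns model form only, if that is what is meant.

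Make an ANCOVA of observed Week 52 scores the main analysis. Under the efficacy estimand, with one planned post-baseline assessment, this means complete cases under missing at random. If the treatment-regimen estimand is chosen, write out an imputation method for these scores. The retrieved-dropout method in 6.12.1.3 is written for HbA1c and extended to body weight in 6.12.2.2, so it cannot simply be cited.

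Remove LOCF from the main analyses in 6.14.1 to 6.14.4. If it is kept, make it a sensitivity analysis with the endpoint labelled Week 52 or early termination.

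The change is SAP wording and needs no new data. The cost is that participants with only an early-termination score leave the main analysis or are imputed.
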